9.1.2 POWER ANALYSIS

From our 4-person pilot study of persons with Alzheimer's Disease, we calculated the average HCP-standardized functional connectivity levels of right TGd with all areas that had non-zero functional connectivity. The mean was 0.096 with a pooled standard deviation of 0.033. Given this limited preliminary data, we will consider a one standard deviation (0.033) change from baseline to be meaningful. With 10 subjects, we have 80% power to detect a 0.033 change from baseline if the pooled standard deviation remains similar to our preliminary findings.

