2.2.2 KNOWN POTENTIAL BENEFITS

Benefits for the patient include the ability to review imaging of their rs-fMRI imaging studies. In addition, patients may experience improvements in mood or cognition with the TMS although this has not been well-established at this time.

This research will be important to better investigate the role of non-invasive neurostimulation for symptoms in AD in a larger cohort and will support a future application for an NIH-sponsored grant.

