5 STUDY POPULATION

The study will enroll 10 subjects with a diagnosis of early stage AD (mild cognitive impairment or mild AD). Those patients where fMRI is contraindicated (e.g. implantable device, pacemaker, metallic implants, etc.) or who are unable to tolerate sitting for a one-hour fMRI will be excluded from the study.

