7.3 LOST TO FOLLOW-UP

The reason for participant discontinuation or withdrawal from the study will be recorded on the relevant CRFs. Subjects who sign the informed consent form and undergo only cognitive measures, and not imaging or TMS will not have completed participation and may be replaced.

A participant will be considered lost to follow-up if he or she fails to attend any scheduled study visit and study staff are unable to contact the participant after at least 5 attempts.

The following actions must be taken if a participant fails to attend any required study visit:

- Study staff will attempt to contact the participant, reschedule the missed visit, counsel the participant on the importance of maintaining the assigned visit schedule and ascertain if the participant wishes to and/or should continue in the study.
- Before a participant is deemed lost to follow-up, the investigator or designee will make every effort to regain contact with the participant (where possible, telephone calls or e-mail – if no answer leave a voicemail on the first and last attempt). These contact attempts will be documented.
- Should the participant continue to be unreachable, he or she will be considered to have withdrawn from the study with a primary reason of lost to follow-up.

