9 STATISTICAL CONSIDERATIONS

9.1.1 STATSTICAL PLAN OVERVIEW

The study population demographics (age, race, etc.) will be described using appropriate summary measures (i.e. means, standard deviations, or medians for continuous variables and counts or percentages for discrete variables). Disease characteristics (MMSE and CDR) will also be summarized to describe our population.

The primary aim will be assessed by calculating the difference and corresponding 95% confidence interval between follow-up and baseline connectivity measures of the TGd parcellations. We will conduct a t-test to statistically test if that difference is greater than 0, which would indicate a non-null effect of the TBS intervention on those areas of the brain.

Exploratory aims 1 and 2 will be analyzed similarly to the primary aim.

For exploratory aim 3, parcellations within the DMN, CEN, or SN associated with \geq 4 anomalies on the baseline matrix will be considered for the third TBS treatment. We will descriptively note whether there are shared anomalous parcellations between study patients. If one area of the

brain is anomalous in at least half of the subjects, we will target that area with the third TBS treatment for all patients and analyze it similarly the primary aim. If no such area rises to this level, we will simply describe changes from baseline for the individual areas treated for each patient.

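### The 80% power in section 9.1.2 uses a spread of pilot connectivity levels where the test needs the SD of within-patient change

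*Combined protocol and SAP*

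**What the plan says.** Section 9.1.2 describes the pilot calculation as follows: "we calculated the average HCP-standardized functional connectivity levels of right TGd with all areas that had non-zero functional connectivity". It then reports: "The mean was 0.096 with a pooled standard deviation of 0.033". A change of one such SD is taken as meaningful, and the sample size is justified by one sentence: "With 10 subjects, we have 80% power to detect a 0.033 change from baseline if the pooled standard deviation remains similar to our preliminary findings".

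Section 9.1.1 assesses the primary aim by "calculating the difference and corresponding 95% confidence interval between follow-up and baseline connectivity measures of the TGd parcellations", and adds: "We will conduct a t-test to statistically test if that difference is greater than 0".

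Section 5 sets enrolment at 10. On replacement, section 7.3 covers only consented subjects who "undergo only cognitive measures, and not imaging or TMS will not have completed participation and may be replaced". Section 2.2.2 says that the research "will support a future application for an NIH-sponsored grant".

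**The concern.** The two sections concern different quantities. The test in section 9.1.1 is on a within-patient change, and its power is set by the SD of that change. The SD in section 9.1.2 is reported beside a mean level of 0.096 and describes a spread of levels. The two SDs are linked only through how strongly a patient's two scans agree. By the visit schedule those scans are about nine weeks apart (Weeks 1 and 10), with treatment between them. The documents give no value or assumption for that agreement.

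Two further gaps affect the same figure:

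- Alpha and sidedness are not stated for the power claim, and the test in section 9.1.1 is worded in one direction.
- All 10 patients are assumed to supply both scans. The replacement rule does not reach a patient who was scanned or treated and then lost.

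The power figure is the only reason given for enrolling 10 patients. A reader who checks the plan's own condition, that the pooled SD stays about the same, would wrongly conclude that the 80% had been confirmed.

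**Working it through.** **Inputs from the documents.** n = 10 (sections 5 and 9.1.2); target change 0.033 and SD 0.033 (section 9.1.2); a t-test on follow-up minus baseline, with a 95% confidence interval (section 9.1.1).

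**Not in the documents.** The SD of change, the baseline/follow-up correlation r, the alpha and sidedness of the power claim, and the expected loss. Values of r and the cases of 8 and 9 pairs are therefore assumed ranges.

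**Step 1: reproduce the 80%.** For a paired t-test, T follows a noncentral t distribution with n − 1 degrees of freedom and noncentrality (change / SD of change) × √n. With 0.033 entered as the SD of change:

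- noncentrality = (0.033 / 0.033) × √10 = 3.162
- critical value t(9) = 2.262 (two-sided 0.05)
- power = 80.3%

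This matches the plan. One-sided 0.05 gives about 90%, and a two-sample t-test with 10 per group gives 56.2%; neither matches. Two-sided 0.05 is thus an inference from the match.

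**Step 2: what 80% power requires, whatever was pooled.** Let d be the standardized change that gives 80% power. The largest allowable SD of change is 0.033 / d.

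| Pairs | d, two-sided 0.05 | Largest SD of change | d, one-sided 0.05 | Largest SD of change |
|---|---|---|---|---|
| 10 | 0.996 | 0.0331 | 0.853 | 0.0387 |
| 9 | 1.067 | 0.0309 | 0.909 | 0.0363 |
| 8 | 1.156 | 0.0285 | 0.978 | 0.0337 |

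**Step 3: if 0.033 is a between-patient SD, equal at both scans.** Then SD of change = 0.033 × √(2(1 − r)). For example, at r = 0 it is 0.033 × √2 = 0.0467. The 95% half-width is 2.262 × SD of change / √10.

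| Assumed r | SD of change | Two-sided power, 10 / 9 / 8 pairs | 95% half-width, 10 pairs |
|---|---|---|---|
| 0 | 0.0467 | 51% / 46% / 41% | 0.033 |
| 0.3 | 0.0390 | 66% / 60% / 54% | 0.028 |
| 0.5 | 0.0330 | 80% / 75% / 68% | 0.024 |
| 0.7 | 0.0256 | 95% / 92% / 88% | 0.018 |

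The SD of levels is exactly 0.033 in every row, so the plan's condition is met throughout, yet power with 10 pairs runs from 51% to 95%.

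**Step 4: break-even correlation.** Setting 0.033 × √(2(1 − r)) equal to 0.033 / d gives r = 1 − 1/(2d²). With 10 pairs, two-sided, r = 1 − 1/(2 × 0.996²) = 0.50.

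| Pairs | Break-even r, two-sided 0.05 | Break-even r, one-sided 0.05 |
|---|---|---|
| 10 | 0.50 | 0.31 |
| 9 | 0.56 | 0.39 |
| 8 | 0.63 | 0.48 |

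A one-sided reading does not rescue the claim: at r = 0 with 10 pairs, one-sided power is 66%.

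**The case against.** The strongest reply is that the arithmetic is right and only an assumption is missing. If 0.033 is the SD at each visit and r = 0.5, the SD of change is also 0.033 and the 80% follows. That is true, but it is the same calculation as entering 0.033 as the SD of change. The plan neither states nor supports r = 0.5, and its stated condition says nothing about r. Likewise, a one-sided test at 0.025 also gives 80%, because it has the same upper-tail criterion as two-sided 0.05.

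Several other points stand in part:

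- The meaning of *pooled* is not given. If it is a spread over connections, the formula in r does not apply and the direction of any error is unknown. The limits in Step 2 hold under every reading.
- The 95% confidence interval and the reference in section 9.1.1 to a non-null effect favour a two-sided reading. Stating it would settle the matter.
- The study is a pilot, its aims are to estimate, and section 9.1.2 concedes that the pilot data are limited. That caveat warns that the SD is imprecise. It does not tell the reader that the SD is of a different kind.
- The SD of change could be recovered from the planned interval and n, so naming it as an output adds little. The correlation could not be recovered that way.

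**Conclusion.** The concern holds. The 80% is correct for the number entered, but that number is described as a spread of levels and was used as an SD of change. Keeping the pooled SD near 0.033 therefore does not secure 80% power.

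The firm result is that the SD of change must not exceed 0.0331 with 10 pairs, 0.0309 with 9 or 0.0285 with 8 (two-sided 0.05). The range of 51% to 95% rests on three assumptions: 0.033 is a between-patient SD, it is equal at both scans, and r lies between 0 and 0.7. Even with the SD of change at 0.033, losing one pair gives 75% and losing two gives 68%.

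The documents do not show that true power is below 80%; if r exceeds about 0.5, it is higher. What fails is the support for the only sample-size justification in the plan. It should be fixed.

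**What to change.** Replace the power sentence in section 9.1.2 with wording such as: *With 10 evaluable pairs of scans, the paired t-test has 80% power to detect a mean change of 1.0 SD of the within-patient change (two-sided 0.05). The pilot SD of 0.033 was calculated over [state what was pooled] and is not an SD of change.* If the sponsor does hold repeat pilot scans, it should give the SD of change from them instead of the second sentence.

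Also:

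- Confirm or correct the two-sided 0.05, and make the test wording in section 9.1.1 agree with it.
- Give power and expected 95% half-width for 8 to 10 evaluable pairs over a range of SD of change. If 0.033 is a between-patient SD, express that range as r = 0 to 0.7.
- As an optional addition, name the observed SD of change and the baseline/follow-up correlation as planned outputs. They are the planning inputs for the later grant application.

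The cost is wording only, with no added patients and no change of endpoint or test. The stated power becomes conditional and may look less favourable. On the between-patient reading it is below 80% if r is under about 0.5 with 10 pairs, or at r = 0.5 with any loss (both two-sided).

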10 SUPPORTING DOCUMENTATION AND OPERATIONAL CONSIDERATIONS

10.1 REGULATORY, ETHICAL, AND STUDY OVERSIGHT CONSIDERATIONS

10.1.1 INFORMED CONSENT PROCESS

All research study staff will maintain certification in human subject's protection. All study investigators and staff will take an active role in developing procedures to protect against or minimize potential risks to the safety and well-being of enrolled participants. Potential research subjects will be informed that participation in this study is voluntary and will not be discriminated against if they choose not to participate. Written informed or electronic consent and assent will be obtained from participants, and family member/caregivers or legally authorized representatives (LAR). Participants will be asked to describe in their own words the study's expectations. Subjects will be informed that they can withdraw from the study at any time and will be given a copy of the consent form. Subjects will have written assurance that while de-identified individual subject data may be available to other researchers for research purposes, or used to improve the software program, only a summary of the results will ever be published or otherwise publicly released. Subjects will be assured that participation in the study will be strictly confidential, that any identifying information will be available to the study staff only, and that no identifying information concerning the data and results will be made known.

Potential research subjects will be informed that participation in this study is voluntary and that their decision to participate will not reflect upon their relationships with the Center for Memory and Aging, Regions Hospital, or HealthPartners. Subjects will be informed that they can withdraw from the study at any time and will be given a copy of the consent form.

With the electronic consent via REDCap the patient/caregiver providing consent will be able to review the consent form themselves and sign electronically with a stylus, touch screen, or cursor

using a signature field in REDCap. After the individual has received the link and can view the consent form, the research staff member will go through the consent form with the individual as would be typical in person. Following the consent conversation, the staff member will sign and e-mail the consent and HIPPA electronically to the patient. The patient will electronically sign, certify, and submit the consent and HIPPA in REDCap. A fully executed PDF copy of the consent and HIPPA will be provided electronically to the patient for their records as well as saved via the auto-archiver function in REDCap.

10.1.2 STUDY DISCONTINUATION AND CLOSURE

This study may be temporarily suspended or prematurely terminated if there is sufficient reasonable cause. Written notification, documenting the reason for study suspension or termination, will be provided by the suspending or terminating party to regulatory authorities. If the study is prematurely terminated or suspended, the Principal Investigator (PI) will promptly inform study participants, the Institutional Review Board (IRB). Study participants will be contacted, as applicable, and be informed of changes to study visit schedule.

Circumstances that may warrant termination or suspension include, but are not limited to:

- Determination of unexpected, significant, or unacceptable risk to participants
- Insufficient compliance to protocol requirements
- Data that are not sufficiently complete and/or evaluable

Study may resume once concerns about safety, protocol compliance, and data quality are addressed.

10.1.3 CONFIDENTIALITY AND PRIVACY

Participant confidentiality and privacy is strictly held in trust by the participating investigators, their staff, the safety and oversight monitor(s), and the sponsor(s). This confidentiality is extended to the data being collected as part of this study. Data that could be used to identify a specific study participant will be held in strict confidence within the research team. No personally-identifiable information from the study will be released to any unauthorized third party without prior written approval of the sponsor/funding agency.

All research activities will be conducted in as private a setting as possible.

All study regulatory binders will be stored in a locked file cabinet within a secure office. The internal study monitor, representatives of the IRB, or regulatory agencies, may inspect all documents and records required to be maintained by the investigator, for the participants in this study. The clinical study site will permit access to such records.

The study participant's contact information will be securely stored at the clinical site for internal use during the study. At the end of the study, all records will continue to be kept in a secure location for as long a period as dictated by the reviewing IRB, Institutional policies, or sponsor/funding agency requirements.

A unique study ID code unrelated to the medical record number or other study subject-specific information will be assigned to each patient and used to link data from various sources and needed for analysis. The study number will be used on the RedCap database and Infinitome Program. All imaging data uploaded from the NSC research site will be de-identified and uploaded to the Infinitome cloud-based server.

Infinitome program uses an industrial grade cyber security that is superior to what is offered at the leading medical device companies. No personal health information is stored on servers and only de-identified scans are stored on a dedicated edge node on encrypted MinIO instances. Patient data is only accessed through authenticated calls form Kubernetes pods contained in the VPC. The web service requires user authentication. Only the data related to a specific facility can be retrieved through authenticated calls and are restricted to their use

The PI will ensure all mechanisms used to share data will include proper plans and safeguards for the protection of privacy, confidentiality, and security for data dissemination and reuse (e.g., all data will be thoroughly de-identified and will not be traceable to a specific study participant). Plans for archiving and long-term preservation of the data will be implemented, as appropriate.

10.1.5 SAFETY OVERSIGHT

There is no Data Safety Monitoring Board for this study, as the risks are minimal. We plan to have a data safety officer (DSO), who will be an independent individual and is not participating in the trial and have no direct affiliation with the research team. The DSO responsibilities include but are not limited to the following:

- Monitoring the study for compliance to the protocol.
- Stopping the study if the rate of SAE's raises safety concerns.

Frequency of the DSO meetings, responsibilities, and procedures will be documented prior to initiation of the study.

10.1.6 CLINICAL MONITORING N/A, refer to next section

10.1.7 QUALITY ASSURANCE AND QUALITY CONTROL

Study staff will perform internal quality management of study conduct, data collection, documentation and completion.

Quality control (QC) procedures will be implemented as follows:

Informed consent --- Study staff will review both the documentation of the consenting process and 10% of the completed consent documents. Feedback will be provided to study staff to ensure proper consenting procedures are followed.

Protocol Deviations – The study team will review documented protocol deviations on an ongoing basis and will implement corrective actions when the quantity or nature of deviations are deemed to be at a level of concern.

Should independent monitoring become necessary, the PI will provide direct access to all study related sites, source data/documents, and reports for the purpose of monitoring and auditing by the sponsor/funding agency, and inspection by local and regulatory authorities.

10.1.8 DATA HANDLING AND RECORD KEEPING

10.1.8.1 DATA COLLECTION AND MANAGEMENT RESPONSIBILITIES

Data collection will be the responsibility of the research study staff under the supervision of the PI. The PI will be responsible for ensuring the accuracy, completeness, legibility, and timeliness of the data reported. Data collection/reporting tools will be developed internally (i.e. CRFs or eCRFs (RedCap Database) and source documents). Data collected and stored electronically will remain confidential and secure (e.g. secured server, encrypted data, password protected file).

10.1.8.2 STUDY RECORDS RETENTION

Investigator records will be retained in accordance with regulatory, organizational and sponsor or grantor requirements. All records will be maintained securely with limited access. Disposal of investigator records will be done in such a manner that no identifying information can be linked to research data.

10.1.9 PROTOCOL DEVIATIONS

Plans for detecting, reviewing, and reporting deviations from the protocol should be described. A This protocol defines a protocol deviation as any noncompliance with the study protocol. The noncompliance may be either on the part of the participant, the investigator, or the study site staff. As a result of deviations, corrective actions will be developed by the site and implemented promptly.

10.1.10 PUBLICATION AND DATA SHARING POLICY

This study will be registered at ClinicalTrials.gov, and results information from this study will be submitted to ClinicalTrials.gov. In addition, every attempt will be made to publish results in peer-reviewed journals.

Data from the de-identified images may be utilized by Omniscent for improvement of Infinitome program and potential future imaging research studies.

10.1.11 CONFLICT OF INTEREST POLICY

The study leadership in conjunction with HealthPartners Institute has established policies and procedures for all study group members to disclose all conflicts of interest and will establish a mechanism for the management of all reported dualities of interest.

10.2 ADDITIONAL CONSIDERATIONS N/A

10.3 PROTOCOL AMENDMENT HISTORY

Version	Date	Description of Change	Brief Rationale
1.0	Sep 2 2021		Initial Version
2.0	March 30 2022	Clarification of Number of Treatment sessions per day	In order for subjects to receive the goal 6000 pulses per target per treatment day, they will require a total of 5 sessions per treatment day
2.1	April 26 2022	Clarification of treatment visits over two weeks	The TMS treatment visits have been updated to reflect alternating days. This is to provide flexibility for scheduling visits for patients and easy viewing on the consent. No change in the number of treatment visits
3	May 18 2023	Change in PI -from [name] to [name]	[name] is leaving HP

